Appendix C: Clinical Symptom and Adverse Event Grading Scale

CLINICAL ADVERSE EVENT GRADING SCALE			
Severity	Grade	Definition	
Mild	1	Awareness of symptom, but easily tolerated. Usually transient requiring no special treatment; does not interfere with usual status or activities	
Moderate	2	May be ameliorated by simple therapeutic measures; may interfere with usual activities	
Severe	3	Incapacitating; unable to perform usual activities	
Life-threatening	4	Requires immediate intervention; need for emergency treatment	
Death	5	Resulting in the subsequent death of the subject	

Appendix D: QTc(F) Calculation

The formula is: $QTc(F) = QT/(RR^{1/3})$

- Manually and carefully measure the QT msec (use the longest)
- The "RR interval in seconds" = dividing 60/heart rate
- Power of 1/3 = 0.34
- Take the RR and elevate it to the power of 0.34
- Divide the QT by that number

Example:

For a QT of 400 msec and a heart rate of 80 bpm

RR interval =
$$60/\text{heart rate} = 60/80 = 0.75$$

$$0.75^{0.34} = 0.9$$

$$400/0.9 = QTc(F) = 444 \text{ msec}$$

The QTc(F) for a QT of 400 msec and a heart rate of 80 bpm is 444.

Appendix E: Topical Steroid Potency Chart

The following potency chart categorizes brand- name topical steroid medications along with the name of the corresponding generic drug. The medications are listed in order of their potency. Please note that the percentage of ingredient in the medication does not necessarily correlate with the strength of the steroid. The list may not be comprehensive.

Brand Name	Generic Name			
Class 1 – Superpotent				
Clobex Lotion/Spray/Shampoo, 0.05%	Clobetasol propionate			
Cormax Cream/Solution, 0.05%	Clobetasol propionate			
Diprolene Ointment, 0.05%	Augmented betamethasone			
Olux E Foam, 0.05%	Clobetasol propionate			
Olux Foam, 0.05%	Clobetasol propionate			
Temovate Cream/Ointment/Solution, 0.05%	Clobetasol propionate			
Ultravate Cream/Ointment, 0.05%	Halobetasol propionate			
Vanos Cream, 0.1%	Fluocinonide			
Cordran Tape, 0.05%	Flurandrenolide			
Class 2 - Potent				
Diprolene Cream AF, 0.05%	Augmented betamethasone			
Elocon Ointment, 0.1%	Mometasone furoate			
Florone Ointment, 0.05%	Diflorasone diacetate			
Halog Ointment/Cream, 0.1%	Halcinonide			
Lidex Cream/Gel/Ointment, 0.05%	Fluocinonide			
Psorcon E Cream, 0.05%	Diflorasone diacetate			
Topicort Cream/Ointment, 0.25%	Desoximetasone			
Topicort Gel, 0.05%	Desoximetasone			
Class 3 – Upper Mid-Strength				
Cutivate Ointment, 0.005%	Fluticasone propionate			
Lidex-E Cream, 0.05%	Fluocinonide			
Luxiq Foam, 0.12%	Betamethasone valerate			
Topicort LP Cream, 0.05%	Desoximetasone			
Class 4 – Mid-Strength				

Flurandrenolide Mometasone furoate Triamcinolone acetonide
Triamcinolone acetonide
Fluocinolone acetonide
Hydrocortisone Valerate
Fluocinolone acetonide
Flurandrenolide
Fluticasone propionate
Prednicarbate
Desonide
Hydrocortisone butyrate
Hydrocortisone probutate
Fluocinolone acetonide
Hydrocortisone valerate
Alclometasone dipropionate
Fluocinolone acetonide
Desonide
Fluocinolone acetonide
Desonide
Hydrocortisone

Abstracted from: National Psoriasis Foundation. Topical treatments for Psoriasis. 2013. http://www.psoriasis.org/document.doc?id=164 (accessed 24 February 2014).

PFS-6	progression-free survival at 6 months
PK	Pharmacokinetics
PR	Partial response
PT	Preferred Term
RANO	Response Assessment in Neuro-Oncology criteria
RDI	Relative dose intensity
RV	Residual volume
QD	Once daily
ORR	Overall response rate

Abbreviation	Full Term
QTcF	Corrected QT interval using Fridericia's formula
SAE	Serious adverse event
SAP	Statistical Analysis Plan
SOC	System Organ Class
STB	Stable
TEAE	Treatment-emergent adverse event

1 INTRODUCTION

Tesevatinib (formerly named KD019) was originally developed for a solid tumor indication, and is currently being investigated for the treatment of cancer. In nonclinical studies, tesevatinib selectively inhibited key kinases and validated targets in animal models of polycystic kidney disease (PKD). In addition, it has shown either no or extremely weak inhibitory activity of other kinases that should reduce off-target effects. Tesevatinib has also been shown to be a potent inhibitor of receptor and cytoplasmic tyrosine kinases (TKs). The product was specifically optimized to simultaneously inhibit EGFR, human epidermal growth factor receptor 2 (HER2), Src, vascular endothelial growth factor receptor 2 (VEGFR2/ KDR), and ephrin receptor B4 (EphB4) tyrosine kinases with high potency, and demonstrated excellent activity in target-specific cellular functional assays. In nonclinical animal models, tesevatinib had acceptable oral bioavailability and has shown sustained inhibition of its targets in vivo following a single oral dose.

In Phase 1 and 2 clinical studies conducted in healthy subjects and subjects with solid tumors, over 300 subjects have been treated to date; at least 185 of these have been treated at levels ≥ 300 mg daily. At least 53 subjects have received tesevatinib for ≥ 6 months, and safety and tolerability were acceptable. Tesevatinib is also in development for the treatment of breast cancer and non-small cell lung cancer (NSCLC).

In summary, both the nonclinical results in PKD models and the clinical safety results in human oncology studies suggest that tesevatinib could be a promising therapeutic in autosomal dominant polycystic kidney disease (ADPKD).

Evaluation of the safety and tolerability data from the subjects in KD019-101 led to the conclusion that tesevatinib 50 mg daily was the dose and schedule most appropriate for use in a randomized study. [REDACTED]

This Statistical Analysis Plan (SAP) describes detailed statistical procedures to be used for study KD019-101 [REDACTED]. KD019-101 is specified in the protocol (Amendment No. 13, 06-Oct-2016): A Phase 2, Multicenter Study of Tesevatinib Monotherapy in Patients with Recurrent Glioblastoma. [REDACTED]

[REDACTED]

The SAP was written in accordance with the recommendations outlined in the International Conference on Harmonisation (ICH) E9 Guideline entitled “Guidance for Industry: Statistical Principles for Clinical Trials” and the most recent ICH-E3 Guideline, entitled “Guidance for Industry: Structure and Content of Clinical Study Reports.”

[figure not shown]
2 STUDY SUMMARY

2.1 Study Objectives

2.1.1 Primary Objectives

2.1.1.1 KD019-101:

- Phase 1b: To determine the safety, plasma pharmacokinetics (PK), and maximum tolerated dose (MTD) of tesevatinib when administered to subjects with ADPKD.
- Phase 2a: To evaluate the annualized change in glomerular filtration rate (GFR) in subjects with ADPKD when treated with tesevatinib.

[figure not shown]

2.1.2 Secondary Objectives

2.1.2.1 KD019-101:

- To evaluate subjects treated with tesevatinib with regard to annualized percent change from baseline in total kidney volume (TKV)
- To evaluate subjects treated with tesevatinib with regard to annualized change from baseline in the reciprocal of serum creatinine

- To evaluate subjects treated with tesevatinib with regard to safety profile
- To evaluate subjects treated with tesevatinib with regard to serum creatinine profiles
- To evaluate subjects treated with tesevatinib with regard to PK and tolerability of 2 alternative dosing schedules (dosing on Monday, Wednesday, and Friday of each week, and dosing on Monday and Thursday of each week)

2.1.3 Post-hoc Objectives:

- To evaluate the slope of the change in the annualized estimated GFR

[figure not shown]
2.2 Study Design

2.2.1 KD019-101

This is a Phase 1b/2a, multicenter, open-label, dose-escalation, safety, MTD, and PK study in subjects with ADPKD. The Phase 1b portion of the study has been completed and the MTD for daily dosing was determined to be 100 mg daily. In this portion of the study, subjects received 50, 100, or 150 mg of tesevatinib orally once daily for 28 days or until the development of unacceptable toxicity, noncompliance, or withdrawal of consent by the subject, or investigator decision. After the initial 28-day safety and tolerability assessment period, subjects may have, at the discretion of the investigator, continued to receive study drug for a total of 24 months from the initiation of treatment.

For those subjects who had received a minimum of 6 months of treatment at the 50 mg/day dose, dose escalation to 100 mg/day was allowed after the 100 mg/day was evaluated for safety.

In order to study the safety profile in this specific ADPKD subpopulation, up to 50 additional subjects with PKD and baseline eGFR ≥ 35 mL/min/1.73 m² and ≤ 80 mL/min/1.73 m², and htTKV ≥ 1000 mL will be enrolled (SILK Cohort). Up to 50 subjects will be enrolled and required to complete PK testing as described for other Phase 2a subjects in this protocol or iothalamate testing.

2.3 Visit Schedule and Study Assessment

The flow chart of visit schedule and study assessments is given in Table 4-1 of the KD019-101 Protocol [REDACTED].

3 STATISTICAL METHODS

3.1 General Methods

3.1.1 Computing Environment

All statistical programming and data analyses will be performed using SAS® Version 9.4 on Windows platform.

3.1.2 Sample Size Justification and power calculations:

Eight subjects per cohort is a standard and reasonable sample size for determination of safety in this Phase 1b portion of the study. Given the frequency and timing of the most common AEs in prior clinical studies of tesevatinib, 8 treated subjects per dose is sufficient to describe the safety profile of tesevatinib in this subject population. These subjects who receive 50 mg daily of tesevatinib will provide 75% likelihood of having at least 1 AE if the true incidence of an AE is 5%.

In the Phase 2a cohort, the 65 subjects in the 50 mg QD dose group will allow an 80% confidence interval of approximately ± 0.64 mL/min about an expected mean 6-month change from baseline of -2.5 mL/min when the standard deviation is 4.0 mL/min.

3.1.3 General Considerations

General considerations for descriptive statistics and presentation for continuous and categorical data are given below.

3.1.3.1 Continuous variables

Continuous data will be described using descriptive statistics: number of observations (n), mean, standard deviation, median, minimum, and maximum.

Means, medians, standard deviations, and confidence intervals (CIs) will be reported to one decimal place more than the data reported on the case report form (CRF) or by the vendor. Minimum and maximum will be reported to the same number of decimal places displayed on the CRF or by the vendor. P-values will be reported to 4 decimal places.

3.1.3.2 Binary Endpoint and Other Categorical Variables

For endpoints with two possible outcomes such as alive/otherwise or response/otherwise within specific periods, the 95% confidence interval will be calculated with Clopper-Pearson method for survival rates or response rates. For other categorical variables, the counts and percent of each category within a parameter will be calculated for observed data only. The denominator for all percentages, unless otherwise specified, will be the number of subjects in the cohort or in the specified analysis population.

3.1.4 Study Day

The Study Day for all assessments prior to the first study drug administration is calculated as the difference between the date of the event or measurement (e.g., adverse event [AE] onset date, assessment date, sample collection date) and the start date of study treatment. The day before the start of study treatment is Study Day -1.

The Study Day for all post-assessments after the first study drug administration is calculated as the difference between the date of the event or measurement (e.g., AE

onset date, assessment date, sample collection date) and the start date of study treatment plus one day. The first day of study treatment is Study Day 1.

3.1.5 Baseline

Baseline value is defined as the valid and last non-missing value obtained within 28 days prior to subject receiving the first study medication, unless otherwise stated under the related assessment section. Baseline can be the day before the first study medication or on the same day as the first study medication if a pre-dose assessment is available. Subjects without data on a parameter before the first study medication will have a missing baseline for this parameter.

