11.3.3.1 Response to QTc(F) Interval Prolongation

The following guidelines should be used in the management of QTc(F) prolongation. Subjects will have ECGs performed at times designated by the protocol (ECGs will be repeated 3 times consecutively within 30 minutes [must have an interval of at least 1–2 minutes between ECGs]). If the average QTc(F) interval increases to > 60 msec above the highest average predose value (average of Day 1 predose and screening values) or to the level of ≥ 480 msec according to local site analysis:

• Hold study drug until central read is confirmed.

- Check electrolytes, especially magnesium and potassium; correct abnormalities as clinically indicated.
- Obtain blood sample for PK analysis.
- Manage as clinically indicated with cardiology consultation as needed.
- Contact medical monitor to discuss additional monitoring.

If results are confirmed by the central reader, the subject may be removed from the study after discussion with the medical monitor. If the subject continues in the study, discuss with the medical monitor appropriate management (including possibility of dose reduction) and ECG follow-up.

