3.8.4 ECG

Descriptive statistics for ECG parameters (i.e., PR interval, QRS interval, and QTcF interval) at each time point with triplicate ECGs will be presented for the values and change from baseline scores. (QTcF is the QT interval using Fridericia's correction which is calculated by $QTcF = QT/RR^{1/3}$.)

The number and percentage of subjects with observed QTcF values that satisfy the following conditions will be presented by treatment group and study visit and categorized as: ≤ 450 ms; > 450 to 480 ms; > 480 to 500 ms; and > 500 ms.

The number and percentage of subjects having change from baseline QTcF values that satisfy the following conditions will be presented by treatment group and study visit and categorized as: ≤ 0 ms; > 0 to ≤ 30 ms; > 30 to ≤ 60 ms; and > 60 ms.

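### The SAP's QTcF change-from-baseline tables default to the last pre-dose value, not the screening/Day 1 average behind the protocol's >60 msec criterion, so the reference is noisier and the counts may differ

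*SAP*

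**What the plan says.** - **SAP 3.1.5 (Baseline)** gives the general rule: "Baseline value is defined as the valid and last non-missing value obtained within 28 days prior to subject receiving the first study medication". It applies "unless otherwise stated under the related assessment section". A same-day value counts if it was taken before dosing.
- **SAP 3.8.4 (ECG)** gives descriptive statistics "at each time point with triplicate ECGs will be presented for the values and change from baseline scores". On the categories, which are split by visit and by group, it says "The number and percentage of subjects having change from baseline QTcF values that satisfy the following conditions will be presented". The top two categories are "> 30 to ≤ 60 ms; and > 60 ms". It does not define a baseline, say how three replicates become one value, or name the local or central read.
- **Protocol 11.3.3.1** judges an average QTc(F) rise of more than 60 msec "above the highest average predose value (average of Day 1 predose and screening values"), "according to local site analysis", with the central read used to confirm.
- **Elsewhere the protocol's wording varies.** The synopsis (Pharmacokinetics) uses a plain average of Day 1 predose and screening for the PK-sample trigger. The visit notes (for example 9.2.2.2) and 9.13 refer to the highest average predose reading. Section 9.10 says only baseline, on the central analysis. Table 4-1 says baseline in footnote g and average baseline in footnote m.
- **SAP 3.8** keeps unscheduled visits out of the summary tables; they appear only in listings.

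**The concern.** The SAP allows an assessment section to override its default baseline, and the ECG section does not do so. The default therefore governs the QTcF change tables. For a subject with a Day 1 predose ECG, the screening ECG plays no part, whereas the protocol's >60 msec criterion brings it in.

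Two consequences follow. First, the >60 ms row looks like a count of subjects meeting the protocol's criterion but is measured from a different reference. Second, a baseline from one time point carries more error than an average over two. That widens the distribution of change and pushes more subjects into the upper categories.

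QTc is a toxicity of special interest. Protocol 5.2.2.2.3 and 14.1 record that moderate QTc prolongation in 2 subjects at 100 mg led to the focus on 50 mg, and 14.3.8 asks for QTc(F) prolongation to be summarised separately. Readers will look closely at these rows.

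**Working it through.** The documents state no figure for this point, so there is none to reproduce.

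**Inputs**
- Three ECGs per time point: Protocol 9.10.
- Mean QTcF rise of 13.3 ms at the mean Cmax for 50 mg: Protocol 5.3.1. This is near the peak; the same section gives a time-averaged rise of 4–6 ms.
- N = 65 at 50 mg daily: SAP 3.1.2.
- Between-visit SD *v* and replicate SD *r*: **assumed**, as (v, r) = (5, 5), (6, 4), (8, 6), (10, 8), (12, 10) ms. Errors are taken as normal, independent and of equal variance across visits.

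**Formulas.** The error variance of one visit's triplicate mean is V = v² + r²/3. The post-dose value is taken as a triplicate mean throughout.

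- A, single last replicate as baseline: Var(change) = V + v² + r²
- B, Day 1 triplicate mean as baseline: Var(change) = V + V = 2V
- C, mean of screening and Day 1 triplicate means: Var(change) = V + V/2 = 1.5V

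B against C does not depend on the SDs. The variance ratio is 2/1.5 = 1.333 and the SD ratio is √1.333 = 1.155. Moving from B to C cuts error variance by 25% and SD by 13%.

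**SD of change (ms)**

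| (v, r) | V | A | B | C | A/C |
|---|---|---|---|---|---|
| (5, 5) | 33.33 | 9.13 | 8.16 | 7.07 | 1.29 |
| (6, 4) | 41.33 | 9.66 | 9.09 | 7.87 | 1.23 |
| (8, 6) | 76.00 | 13.27 | 12.33 | 10.68 | 1.24 |
| (10, 8) | 121.33 | 16.89 | 15.58 | 13.49 | 1.25 |
| (12, 10) | 177.33 | 20.53 | 18.83 | 16.31 | 1.26 |

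A exceeds C by 23–29% over these pairs. Other combinations fall outside that range: (12, 4) gives 18% and (5, 10) gives 45%.

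**Chance of exceeding 30 ms from this noise**, P = 1 − Φ((30 − 13.3)/SD):

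| (v, r) | A | B | C |
|---|---|---|---|
| (6, 4) | 4.2% | 3.3% | 1.7% |
| (8, 6) | 10.4% | 8.8% | 5.9% |
| (10, 8) | 16.1% | 14.2% | 10.8% |

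**Chance of exceeding 60 ms**, P = 1 − Φ((60 − 13.3)/SD). At (10, 8) this is 0.28% (A), 0.14% (B) and 0.03% (C). In 65 subjects that is 0.19, 0.09 and 0.02 expected at one visit.

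A simulation (1,000,000 draws per scenario) used the pairs (5, 5), (8, 6), (10, 8) and (12, 10), with a between-subject SD of drug effect of 0 or 10 ms (also assumed). Expected >60 ms counts at one visit were 0.00–0.93 under B and 0.00–0.48 under C. If d is the chance that B and C classify a subject differently, the chance of at least one difference in 65 is 1 − (1 − d)^65. The largest d was 0.01137, giving 1 − 0.98863^65 = 0.525, so the range is about 0–53%.

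If *highest average* means the larger of the two predose averages, the rule's reference shifts upward and it flags fewer subjects than C. In the noisiest scenario this is 0.32% against 0.73%.

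**The case against.** The strongest reply is that a management trigger and a descriptive table need not share a baseline, and no document says these tables reproduce the trigger. No test or decision hangs on them, and 50 mg had already been selected. That limits the stakes, but it does not explain a less precise baseline when the second ECG is already collected and the protocol's own criterion uses it.

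Four stronger readings are tempting and are not supported:

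- **That the SAP baseline is one replicate.** This is the literal sense of a last value, but SAP 3.8.4 refers to triplicate ECGs and is silent on combining them. A Day 1 triplicate mean is at least as natural, and the 15% figure belongs to it.
- **That the tables will disagree with the protocol's criterion.** At the 13.3 ms mean, the >60 ms row would often coincide. The effect is clearer above 30 ms, where the protocol has no action rule.
- **That the protocol has one clean reference which the SAP contradicts.** Its wording varies, as shown above.
- **That changing the baseline would make the tables reproduce the hold events.** Holds start from local reads, and unscheduled ECGs are left out of the tables.

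A reader might also want the absolute bands moved because 480 ms falls below the SAP's upper band while the protocol acts at ≥480 msec. That affects only values of exactly 480 and is a reporting preference.

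**Conclusion.** The point holds in a limited form. By its stated default, the SAP measures QTcF change from the last pre-dose value and discards the screening ECG when a Day 1 predose ECG exists. Protocol 11.3.3.1 and the synopsis PK trigger use an average of the two.

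The error SD of change is therefore about 15% higher than with the two-visit average on the favourable reading, given equal, independent errors at the two visits. It is about 23–29% higher on the single-replicate reading, over the assumed SD pairs. The >30 ms proportions above describe measurement noise around a fixed mean near the peak effect; at trough visits they would be smaller. A mismatch in the >60 ms row is possible but not certain. This affects safety tabulation, not the primary endpoint.

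**What to change.** 1. In SAP 3.8.4, define the QTcF baseline as the mean of the screening and Day 1 predose triplicate means, on the central read. Use the triplicate mean, also on the central read, at every post-dose time point.
2. Reconcile the protocol's reference wordings (highest average, average, undefined baseline) so that one definition can be cited. Which of them governs clinical action is for the sponsor to settle; the SAP definition is for reporting only.
3. Add a table note that the counts can still differ from the hold events, because holds start from local reads and unscheduled ECGs appear only in listings.

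The cost is wording and programming. The ECGs are already scheduled, so no new data are needed.

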3.1.6 Handling of Incomplete or Missing Data

Missing data will not be imputed in general and will be reported as missing in all listings. For categorical variables, patients with missing data are not included in calculations of percentages unless otherwise specified.

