14 STATISTICAL CONSIDERATIONS

All descriptive and inferential statistical analyses will be performed using the most recently released and available SAS statistical software, unless otherwise noted. For categorical variables, the number and percent of each category within a parameter will be calculated for non-missing data. For continuous variables, the mean, median, and standard deviation, as well as the minimum and maximum values, will be presented.

Statistical significance will be declared when the two-tailed p-value is found to be less than or equal to 0.05, unless otherwise noted. Missing data will not be imputed unless otherwise stated. All clinical data captured will be provided in data listings.

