14.3 Statistical Considerations

14.3.1 Study Populations

Adult subjects with ADPKD will be enrolled. The safety population will consist of all subjects who receive at least 1 dose of tesevatinib. An evaluable subject will be defined as one who has completed 28 days (for subjects in the Phase 2a portion of the study this will be 25 or 26 days in the Monday/Thursday and Monday/Wednesday/Friday cohorts, and 28 days in the 50 mg daily dosing cohort). Phase 1b unevaluable subjects (subjects who are not evaluable for toxicity) will be replaced. Subjects who do not complete the study, for whatever reason, will have all available data up until the time of termination related to the reason they were terminated included in the analysis. Completion of the study for subjects enrolled in the Phase 1b portion will be defined as uninterrupted completion of the first 28 days of study drug administration, and completion of the study for subjects entered in the Phase 2a portion of the study will be defined as completion of the Month 6 MRI.

For the Phase 2a cohort, all subjects treated will be included in the analyses based on their available data.

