14.3.6 Efficacy/Activity

Descriptive statistics, including confidence intervals for GFR, will be presented over time for the Phase 2a cohort. In addition, identical statistics for the change and percent change from baseline GFR over time will be presented with the 6-month change from baseline being of particular interest.

Similar descriptive statistics will be presented for the reciprocal of serum creatinine endpoints.

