3.2 Analysis Populations

The following populations will be analyzed:

Modified Intent-to-treat (mITT) Population: The primary population for efficacy analyses will be a Modified Intent-to-treat (mITT) Population. For KD019-101 it is defined as all subjects who completed 28 days (for subjects in the Phase 2a portion of the study this will be 25 or 26 days in the Monday/Thursday and Monday/Wednesday/Friday cohorts, and 28 days in the 50 mg daily dosing cohort).

[REDACTED]

The mITT Population will be used for tables of demography, baseline characteristics, and efficacy.

Safety Population: The Safety Population is defined as all subjects who receive at least 1 dose of tesevatinib.

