3.7 Primary Endpoint Analysis

The primary endpoint for the Phase 1b portion of KD019-101 is safety and tolerability. This will be covered in Section 3.9.

The primary endpoint is annualized change in glomerular filtration rate (GFR) in subjects with ADPKD when treated with tesevatinib. The annualized change in GFR will be calculated as the percent change from baseline divided by total duration in days times 365.25.

This analysis will be done using the mITT population. Descriptive statistics will be provided for each cohort. The annualized GFR will be calculated for the 6, 12, 18 and 24 months timepoints.

GFR will be estimated using three equations; MDRD-4, CKD-EPI_{2012cys}, and CKD-EPI_{2012Scr-cys}.

4-Variable Modification of Diet in Renal Disease (MDRD-4) Equation

High Level Formula for Black or African-American Males:
$\text{Estimated GFR} = 175 \times (\text{Scr}^{-1.154}) \times (\text{Age}^{-0.203}) \times 1.212$
High Level Formula for Males NOT Black or African-American (any other option):
$\text{Estimated GFR} = 175 \times (\text{Scr}^{-1.154}) \times (\text{Age}^{-0.203})$
High Level Formula for Black or African-American Females:

Estimated GFR = $175 \times (\text{Scr}^{-1.154}) \times (\text{Age}^{-0.203}) \times 1.212 \times 0.742$
High Level Formula for Females NOT Black or African-American (any other option):
Estimated GFR = $175 \times (\text{Scr}^{-1.154}) \times (\text{Age}^{-0.203}) \times 0.742$

Note: Age is shown in years. Scr = serum creatinine

CKD-EPI_{2012cys} Equation to Predict Glomerular Filtration Rate (GFR)

Gender	Scys (mg/L)	Equation
Female	≤ 0.8	$133 \times (\text{Scys}/0.8)^{-0.499} \times 0.996^{\text{age}} (\times 0.932)$
	> 0.8	$133 \times (\text{Scys}/0.8)^{-1.328} \times 0.996^{\text{age}} (\times 0.932)$
Male	≤ 0.8	$133 \times (\text{Scys}/0.8)^{-0.499} \times 0.996^{\text{age}}$
	> 0.8	$133 \times (\text{Scys}/0.8)^{-1.328} \times 0.996^{\text{age}}$

Note: Age is shown in years. Scys= serum cystatin

CKD-EPI_{2012Scr-cys} Equation to Predict Glomerular Filtration Rate (GFR)

Gender	Scr (mg/L)	Scys (mg/L)	Equation
Female	≤ 0.7	≤ 0.8	$130 \times (\text{Scr}/0.7)^{-0.248} \times (\text{Scys}/0.8)^{-0.375} \times 0.995^{\text{age}} (\times 1.08, \text{ if black})$
		> 0.8	$130 \times (\text{Scr}/0.7)^{-0.248} \times (\text{Scys}/0.8)^{-0.711} \times 0.995^{\text{age}} (\times 1.08, \text{ if black})$

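### The Phase 2a primary GFR result is a two-point change in whoever still has a value at each timepoint, with no longitudinal model or dropout sensitivity analysis, so the later means could be biased in either direction

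*SAP*

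**What the plan says.** SAP 3.7 defines the measure: "The annualized change in GFR will be calculated as the percent change from baseline divided by total duration in days times 365.25". It sets the timepoints: "The annualized GFR will be calculated for the 6, 12, 18 and 24 months timepoints". It sets the method and population: "This analysis will be done using the mITT population. Descriptive statistics will be provided for each cohort". Under SAP 3.2 that population, for this study, consists of 28-day completers ("it is defined as all subjects who completed 28 days"; 25 or 26 days on the two intermittent schedules).

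On missing data, SAP 3.1.6 says "Missing data will not be imputed in general and will be reported as missing in all listings", and protocol section 14 agrees: "Missing data will not be imputed unless otherwise stated". The SAP's only exceptions are adverse event and medication dates, missing adverse event causality, and event dates.

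The protocol plans the same kind of summary in 14.3.6 ("Descriptive statistics, including confidence intervals for GFR, will be presented over time for the Phase 2a cohort"), with the 6-month change singled out. Its Phase 2a population is wider than the SAP's: "For the Phase 2a cohort, all subjects treated will be included in the analyses based on their available data" (14.3.1).

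Treatment may run to 24 months. Continuing past day 28 is at the investigator's discretion (protocol 7.2), and Phase 2a subjects who discontinue are not replaced (10.3). Central-laboratory tests are monthly to Month 12 (9.2.5, 9.3.3, 9.5.3) and every 2 months after that (9.6). The panels include creatinine and cystatin C (Table 9-1).

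SAP 3.7.2.1 adds a post-hoc MDRD-4 slope built from individual subjects' slopes, once from the first and last values and once from all values.

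**The concern.** A mean at Month 18 or 24 that uses only the subjects still measured describes those who stayed. If staying is related to how fast GFR falls, that mean is not the mean decline of the treated cohort. The study has no control arm, so nothing in the data would separate such selection from a drug effect. The SAP gives no rule for a subject without a value at a timepoint, and no analysis that would show how far the result depends on who left.

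The two-point change also ignores every central-laboratory value between baseline and the timepoint. Those values are already collected, and they carry most of the information about subjects who leave early.

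**Working it through.** **1. The plan's own figure.** Inputs from protocol 14.2 and SAP 3.1.2: n = 65, SD of the 6-month change 4.0 mL/min, expected mean −2.5 mL/min, 80% interval.
- Half-width = 1.2816 × 4.0/√65 = 0.636; with t on 64 df, 0.642. Both give the stated 0.64, which assumes that all 65 are observed.
- With 52, 39 or 26 observed (20, 40 or 60% lost) and the same SD, the half-width is 0.71, 0.82 or 1.01.
- Annualizing doubles the 6-month change, so its SE is 2 × 4.0/√65 = 0.99 mL/min/year.

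**2. Effect of who leaves.** True mean slope: 2 × (−2.5) = −5.0 mL/min/year. The SD of the 6-month change is held at 4.0. Assumptions, because the documents give none: between-subject slope SD 3 or 5 mL/min/year; baseline 57.5 (SD 10); 20, 40 or 60% gone by Month 24; a hazard ratio of leaving per SD worse decline of 1, 1.5, 2 or 0.67. Each scenario simulates 40,000 subjects with monthly values. The table gives the mean of subjects observed at Month 24 when leaving depends on the decline already observed (slope SD 3 / 5):

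| Gone by Month 24 | HR 1 | HR 1.5 | HR 2 | HR 0.67 |
|---|---|---|---|---|
| 20% | −4.98 / −4.97 | −4.80 / −4.59 | −4.65 / −4.44 | −5.24 / −5.40 |
| 40% | −5.00 / −5.01 | −4.53 / −4.22 | −4.19 / −3.61 | −5.48 / −5.87 |
| 60% | −5.00 / −5.05 | −4.14 / −3.52 | −3.60 / −2.73 | −5.85 / −6.48 |

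- At hazard ratio 2 the error runs from 5.00 − 4.65 = 0.35 to 5.00 − 2.73 = 2.27 mL/min/year. At the assumed baseline of 57.5, that is 0.6 to 3.9 percentage points per year on the SAP's percent scale.
- At Month 6 the error in the same scenarios is at most 5.00 − 4.28 = 0.72.
- A random-intercept, random-slope likelihood estimate on all visits (variances treated as known) gives −4.97 to −5.04 in every cell.
- If leaving depends instead on the unobserved true slope (40% gone, hazard ratio 2), the Month 24 mean is −4.11 to −3.42 and the mixed model −4.63 to −4.52. The model then removes only part of the bias.

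**3. What the unused values add to precision.** Assume full retention. Residual variance r follows from 4.0² = 2r + 0.25 × (slope SD)², so r = 6.875 (slope SD 3) or 4.875 (slope SD 5). The variance of the mean two-point change over T years is (slope SD² + 2r/T²)/65. For the all-visit slope it is (slope SD² + r/Sxx)/65. Sxx is 0.194 year² for monthly values to Month 6, and 6.57 year² for monthly values to Month 12 and then every 2 months to Month 24.

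| | Two-point SE | All-visit SE |
|---|---|---|
| to Month 6 | 0.99 | 0.83 / 0.88 |
| to Month 24 | 0.44 / 0.65 | 0.39 / 0.63 |

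Like for like, the gain is modest at Month 6 and small at Month 24. Most of the difference from the 6-month SE of 0.99 comes from longer follow-up.

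**4. The acute creatinine rise.** Protocol 5.2.2.2.3 reports median creatinine up 22% at Day 7 and 13% at Day 28 on 50 mg, with no rise in cystatin C. A fixed 13% rise changes MDRD-4 eGFR by 1.13^(−1.154) − 1 = −13.2%. The SAP formula turns this into −26.3, −13.2, −8.8 and −6.6% per year at 6, 12, 18 and 24 months. Under MDRD-4 the later timepoints look better even with no dropout.

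**The case against.** The strongest objection concerns direction. A reader might infer that subjects who decline drop out and that the late means are therefore too favourable. The documents do not support this. Protocol 10.1 does not name GFR decline among the reasons for withdrawal. The withdrawals that the protocol describes, 3 of 5 in the 150 mg daily cohort, were mainly over rash. Leaving for toxicity is not leaving for GFR decline. The table shows no bias at hazard ratio 1 and the opposite bias at 0.67. This objection stands in full.

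A reader might also call the analysis complete-case. It is available-case at each timepoint: a subject who leaves at Month 14 still counts at Months 6 and 12. The SAP does not define the duration used for annualizing. If it meant each subject's own last value, early leavers could enter later summaries as well.

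The post-hoc slope on all values uses the repeated measurements and includes early leavers who have post-baseline data. That is a real mitigation, but a partial one. It is post-hoc and MDRD-4 only, and it summarises individual slopes with no stated weighting, so a short, noisy slope may count as much as one over 24 months.

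The 6-month change is the one the protocol stresses, and the analysis is descriptive. Both facts limit the consequence. They do not remove it, because SAP 3.7 makes the 12-, 18- and 24-month summaries part of the primary endpoint. A large precision gain from the unused data would also be an over-reading, as step 3 shows.

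**Conclusion.** The gap is real and its direction is unknown. The primary GFR summaries at 12 to 24 months depend on who remains, and the SAP has no model or sensitivity analysis to address that. With a true slope of −5 mL/min/year and 20 to 60% dropout, the Month 24 mean is too favourable by about 0.35 to 2.3 mL/min/year if observed decline doubles the hazard of leaving per SD. It is unbiased if leaving is unrelated to GFR, and too unfavourable if better-preserved subjects leave. The dropout rates, hazard ratios, slope SDs and baseline are assumptions; only n, the expected change and its SD come from the documents.

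The consequence is a possibly biased descriptive mean in a single-arm study. It is not an inflated type I error. The size and sign cannot be settled from the documents, so this is a cheap improvement to the SAP.

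**What to change.** - **Main estimate.** Report the mean slope in mL/min/1.73 m² per year with its confidence interval, from a linear mixed model with random intercept and slope. Use all on-drug eGFR values from all treated Phase 2a subjects, which restores the population rule in protocol 14.3.1.
- **Acute creatinine effect.** Use the CKD-EPI 2012 cystatin C equation as the main version, or start the slope after the acute step. Exclude off-drug values from the SILK drug holiday.
- **Supportive summaries.** Keep the 6-, 12-, 18- and 24-month descriptives, with n and reasons for missingness at each. Define the duration used for annualizing.
- **Sensitivity.** Add one not-at-random analysis, for example delta-adjusted, because the mixed model corrects only part of the bias if leaving depends on the unobserved slope.

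The cost is SAP wording, one standard model and one sensitivity run, with no new data collection. The downside is that the model assumes missing-at-random and near-linear decline after the acute step.
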